10.3 Analysis Sets

For the purposes of analysis, the following populations are defined:

Table 10.3-1: Populations for Analysis

Population	Description
Intent-to-Treat	The ITT analysis population will consist of all randomized participants from the screened analysis population that receive at least 1 dose of IP. Participants in the ITT analysis population will be analyzed according to the randomized treatment, regardless of the treatment received.
Safety	The safety analysis population is defined as all participants who are randomized and receive at least 1 dose of IP, analyzed by actual treatment received.
PK	The PK population will consist of ITT participants who have at least 1 post-Screening PK assessment.
Randomized	All participants who were randomized using IRT.

Protocol Amendment No.: 02

^a CI obtained assuming an estimated ozanimod Week 12 clinical remission (CDAI<150) rate of 33.3%. The normal approximation for constructing the 95% CIs may produce an unusually conservative lower bound for sample sizes under 100.

Table 10.3-1: Populations for Analysis

Population	Description
Per-protocol	The PP population will consist of all participants in the ITT population. Those participants who have specific reasons for warranting exclusion from this population will be documented prior to database lock and may include but are not limited to protocol deviations that substantially affect the key efficacy endpoint.

Abbreviations: IP, investigational product; IRT, integrated response technology; ITT, intent-to-treat; PK, pharmacokinetic; PP, per-protocol.

The primary analysis population for all efficacy endpoints will be the intent-to-treat (ITT) analysis population. All safety analyses will be carried out on the Safety population. The PK analyses will be carried out on the PK population. The selected efficacy/safety analysis will be carried out on the PP population as specified.

Participant demographics will be summarized for the ITT population and will include age, sex, race, ethnicity, height, weight, and BMI.

Baseline characteristics will be summarized for the ITT population and will include age at CD symptom onset, age at CD diagnosis, years since CD symptom onset, years since CD diagnosis, prior anti-TNF use, corticosteroid use at Screening, concomitant CD medication use at Baseline, each component of the CDAI score, and PCDAI. Participants should continue to be assessed for PCDAI throughout the trial, regardless of age change.

Compliance with randomized IP will be summarized and will include the number of participants estimated to be < 80% compliant, 80% to 100% compliant, > 100% compliant, and > 120% compliant.

10.4 Statistical Analyses

10.4.1 General Considerations

This is a global, multicenter, randomized, double-blind Phase 2/3 study to evaluate the efficacy, safety, and tolerability of ozanimod in pediatric participants aged 2 to 17 years inclusive with moderately to severely active CD, defined as a PCDAI score of \geq 30, SES-CD score of \geq 6 (or SES-CD \geq 4 in participants with isolated ileal disease), with an inadequate response, intolerance, or loss of response to conventional therapy for CD. The study will also evaluate the PK and PD and evaluate the safety of ozanimod in pediatric participants.

Analysis details not explained in the statistical section of the protocol will be provided in the SAP and PK Analysis Plan.

The detailed definitions of all efficacy endpoints are described in Section 4. Efficacy will be evaluated based on the totality of the data and a comprehensive analysis based on descriptive statistics. Hypothesis testing will not be performed.

The number and percentage of participants in each population will be summarized. Patient disposition, including the number of participants screened, randomized, dosed, completing

Protocol Amendment No.: 02

Week 64, and not completing Week 64 (overall and by reason for dropout), will be summarized for the ITT population.

10.4.2 Primary Endpoint(s)

The primary analyses of the 2 co-primary endpoints, pediatric clinical and endoscopic remission at Week 64, will be based on the ITT population in which all will be pooled. The estimated proportions along with their associated 2-sided 95% Wald CI using a normal approximation for a single sample proportion will be constructed. Summary statistics on the number of events, sample size, and proportions for the overall group and by will also be provided.

For participants whose pediatric clinical and endoscopic remission at Week 64 cannot be adequately determined (including missing data, discontinuation, or lost to follow-up), their missing pediatric clinical and endoscopic remission will be imputed using a non-responder imputation. In addition to the primary overall analysis, a subgroup analysis will be conducted for each of A summary will be tabulated and a forest plot showing the proportions with associated 95% CIs will be produced.

Details on the analyses and the evaluations for the co-primary endpoints will be provided in the SAP, which will include comparisons with the external placebo controls as well as data from ozanimod CD adult trials.

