The primary analyses of the 2 co-primary endpoints, pediatric clinical and endoscopic remission at Week 64, will be based on the intent-to-treat population in which will be pooled. The estimated proportions along with their associated 2-sided 95% Wald confidence intervals (CI) using a normal approximation for a single sample proportion will be constructed.

The analyses of the key secondary endpoint (eg, pediatric clinical remission at Week 12) will be conducted in a similar manner as the co-primary endpoint.

Data Monitoring Committee: Yes

A Data Monitoring Committee will be used in the study.

Other Committee: Yes

Access to treatment assignments will be strictly limited to groups directly involved with drug distribution, preparation of unblinded output for and personnel involved in the conduct of PD assays.

To assure that all personnel involved in the conduct of the study remain blinded to the results of interim reviews, a blinding plan will be specified in the DMC Charter.

Brief Summary:

The purpose of this study is to evaluate the efficacy and safety of ozanimod in pediatric participants with moderately to severely active CD. This will be evaluated by the proportion of participants who achieve PCDAI < 10 at Week 64 and the proportion of participants in endoscopic remission

Protocol Amendment No.: 02

(SES-CD \leq 2 or SES-CD \leq 4 points with no SES-CD subscore > 1 point) at Week 64. Study details include the following:

- Study duration: 81 weeks (excluding LTE period)
- Study intervention duration: 64 weeks
- Study visit frequency: Up to 3 times during the first 8 days of the Induction Period, then every 4 weeks until Week 12, then every 8 weeks starting at Week 20 in the Maintenance Period.

Protocol Amendment No.: 02

[figure not shown]
19

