For the co-primary endpoint of endoscopic remission at Week 64, Table 10.2-2 provides half width (precision) and the expected lower and upper bound of 95% Wald CI of the estimated endoscopic remission rate for overall participants and The calculation assumes a 5.8% endoscopic remission rate for the ozanimod arms (either dose group), which is the estimated ozanimod endoscopic remission rate in study RPC01-2201.

Table 10.2-2: Sample Sizes to Evaluate Week 64 Endoscopic Remission Rates

П		Sample Size	Precision	Expected	Expected
'			(Half-width of	Lower	Upper
			95% CI) ^a	Bound of 95%	Bound of 95%
				CI ^a	CI ^a
				of Ozanimod	of Ozanimod
Г	Overall	100	4.6%	1.22%	10.4%

Abbreviations: Cl, confidence interval.

For the endpoint of proportion of participants achieving clinical remission (CDAI < 150) at Week 12, Table 10.2-3 provides half width (precision) and the expected lower and upper bound of 95% Wald CI of the estimated clinical remission rate for overall participants and The calculation assumes a 33.3% clinical remission rate for the ozanimod arms (either dose group), which is the estimated ozanimod clinical remission rate in study RPC01-2201.

Protocol Amendment No.: 02

^a CI obtained assuming an estimated ozanimod Week 64 clinical remission (CDAI < 150) rate of 21.7%. The normal approximation for constructing the 95% CIs may produce an unusually conservative lower bound for sample sizes under 100.

^a CI obtained assuming an estimated ozanimod Week 64 endoscopic remission rate of 5.8%. The normal approximation for constructing the 95% CIs may produce an unusually conservative lower bound for sample sizes under 100.

Table 10.2-3: Sample Sizes to Evaluate Week 12 Clinical Remission (CDAI < 150)
Rates

	Sample Size	Precision (Half- width of 95% CI ^a)	Expected Lower Bound of 95% CI ^a of Ozanimod	Expected Upper Bound of 95% CI ^a of Ozanimod
Overall	100	9.2%	24.1%	42.6%

Abbreviations: CDAI, Crohn's Disease Activity Index; CI, confidence interval.

The analyses of the key secondary endpoint (eg, pediatric clinical remission at Week 12) will be conducted in the similar manner as the co-primary endpoint (eg, pediatric clinical remission at Week 64). Details will be described in the Statistical Analysis Plan (SAP).

sample size determination for PK evaluation in this study is based on previously published methods.⁴⁵

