Table 10.4.6.3-1: Variables to be Obtained for Each Participant

Measure	Endpoint	
CDAI clinical remission	Proportion of participants who achieve CDAI score < 150 at Week 64	
(adolescents only)	Proportion of participants who achieve CDAI score < 150 at Week 12	
CDAI clinical response	Proportion of participants who achieve CDAI reduction from Baseline of ≥ 100 points or CDAI score < 150 at Week 64	
(adolescents only)	Proportion of participants who achieve CDAI reduction from Baseline of ≥ 100 points or CDAI score < 150 at Week 12	
Corticosteroid-free remission	Proportion of participants who achieve a PCDAI score < 10 at Week 64 while remaining corticosteroid free in the prior 12 weeks	
	Proportion of participants who achieve a CDAI score < 150 at Week 64 while remaining corticosteroid free in the prior 12 weeks (adolescents only)	
Endoscopic remission	Proportion of participants achieving SES-CD < 2 or SES-CD \leq 4 points with no SES-CD subscore > 1 point at Week 12	

Abbreviations: CDAI, Crohn's Disease Activity Index; ER-50, SES-CD decrease from Baseline of ≥ 50%; PCDAI, Pediatric Crohn's Disease Activity Index; SES-CD, Simple Endoscopic Score for Crohn's Disease.

Protocol Amendment No.: 02

Population-Level Summary

For each of the primary and secondary efficacy endpoints, the analysis will be based on the ITT population in which will be pooled. The estimated proportion along with its associated 2-sided 95% Wald CI using a normal approximation for a single sample proportion will be constructed.

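### The 95% Wald interval fixed for the endoscopic co-primary endpoint covers about 92.9% at the plan's own 5.8% and n=100, with an upper limit that is too low

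*Combined protocol and SAP*

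**What the plan says.** The interval method is named in three places. Section 10.4.2, on the two co-primary endpoints: "The estimated proportions along with their associated 2-sided 95% Wald CI using a normal approximation for a single sample proportion will be constructed". The Protocol Summary, under Statistical Methods: "associated 2-sided 95% Wald confidence intervals (CI) using a normal approximation for a single sample proportion". Section 10.4.6.3, under Population-Level Summary: "For each of the primary and secondary efficacy endpoints, the analysis will be based on the ITT population", followed by "The estimated proportion along with its associated 2-sided 95% Wald CI".

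Section 10.4.1 limits what is left open: "Analysis details not explained in the statistical section of the protocol will be provided in the SAP". It also says: "Hypothesis testing will not be performed".

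Section 10.2 takes 5.8% as the Week 64 endoscopic remission rate, from the adult Phase 2 study RPC01-2201. Table 10.2-2 then gives, for n=100, a half-width of 4.6% and expected limits of 1.22% and 10.4%. Its footnote says that the normal approximation "may produce an unusually conservative lower bound for sample sizes under 100". Section 10.4.2 counts participants with undetermined remission as non-responders. It also announces that the SAP will compare the results with external placebo controls and adult ozanimod data.

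**The concern.** The Wald interval centres on the observed proportion and uses a standard error that shrinks as that proportion approaches zero. When few events are seen, the interval is therefore both too low and too narrow. About 6 events are expected for endoscopic remission at n=100, which is where this behaviour shows.

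Because nothing is tested, the interval is the main inferential statement about this co-primary endpoint. If it is labelled 95% but its upper limit falls below the true rate well over 2.5% of the time, readers are told that the plausible range stops earlier than it does. Negative lower limits could also appear in a primary results table. The footnote shows that the plan knows the approximation is weak, but it points the reader to the lower limit and to sample size.

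**Working it through.** **Inputs from the documents.** Two-sided 95% Wald interval (10.4.2); endoscopic rate 5.8% and n=100 (10.2, Table 10.2-2); clinical remission rates 21.7%, 15.8% and 33.3% at n=100 (10.2). The enrolled number is not public, so every n other than 100, and every true endoscopic rate other than 5.8%, is an assumption used to show a range.

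**1. The plan's own figures.** The half-width is 1.96 × √(p(1−p)/n). With p=0.058 and n=100:

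1.96 × √(0.058 × 0.942 / 100) = 4.58%, so the limits are 1.22% and 10.38%. Table 10.2-2 reproduces.

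For clinical remission, the exact binomial probability that the Wald lower limit exceeds the threshold is 89.9% for 21.7% against 9.4% (stated 90%), and 72.9% for 15.8% against 6.8% (stated 73%). These also reproduce.

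**2. Exact coverage at 5.8%, n=100.** Let X be Binomial(100, 0.058). Coverage is the sum of P(X=x) over all x whose interval contains 0.058.

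- Interval wholly below 5.8%: x = 0, 1, 2. At x=2 the limits are −0.7% and 4.7%; at x=3 the upper limit is 6.3%. Probability 0.254% + 1.565% + 4.769% = 6.59%.
- Interval wholly above 5.8%: x ≥ 13. At x=12 the lower limit is 5.6%; at x=13 it is 6.4%. Probability 0.52%.
- Coverage: 100% − 6.59% − 0.52% = 92.89%.
- Negative lower limit: x = 1, 2, 3. Probability 1.56% + 4.77% + 9.59% ≈ 15.9%.

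**3. Other intervals at the same inputs.**

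| Method | Coverage | Wholly below truth | Wholly above truth | 2/100 | 6/100 |
|---|---|---|---|---|---|
| Wald | 92.9% | 6.6% | 0.5% | −0.7 to 4.7% | 1.3 to 10.7% |
| Wilson | 95.1% | 1.8% | 3.1% | 0.6 to 7.0% | 2.8 to 12.5% |
| Clopper-Pearson | 96.9% | 1.8% | 1.3% | 0.2 to 7.0% | 2.2 to 12.6% |

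**4. Is this one unlucky point?** Coverage of a discrete interval oscillates, so ranges matter.

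| Method | 5.8%, every n from 100 to 130 (assumed) | n=100, true rate 4% to 8% in steps of 0.01 point (assumed) |
|---|---|---|
| Wald | 88.2–94.5%, mean 92.1% | 85.1–94.8%, mean 91.6% |
| Wilson | 94.1–97.0%, mean 95.2% | 92.7–97.2%, mean 95.3% |
| Clopper-Pearson | 96.4–97.8%, mean 96.9% | 95.1–98.3%, mean 97.0% |

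Wald does not reach 95% anywhere on either grid; at a true rate of 5% and n=100 it is 87.7%. Its below-truth miss over n=100 to 130 runs from 4.5% to 11.3%.

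**5. The footnote's limit of 100.** At 5.8%, Wald coverage is 93.5% at an assumed n=200 and 92.5% at an assumed n=300. The shortfall does not end at 100.

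**6. Clinical remission.** Wald coverage at n=100 is 94.5% at 21.7%, 95.3% at 15.8% and 95.5% at 33.3%, close to nominal.

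**The case against.** Five points can be made for the plan.

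- **The SAP may say more.** Section 10.4.2 sends details of the co-primary analyses to the SAP, and no separate SAP section appears in the public text. A supplementary exact interval might be planned there. That is possible, but further detail does not reopen a method named three times.
- **The footnote may have been written for removed rows.** The lead-in to Table 10.2-2 mentions groups besides the overall one, and only the n=100 row survives. The footnote may well refer to smaller groups, and it does not say that n=100 is safe. This tempers the criticism of the figure 100. The footnote's silence on the upper limit remains.
- **The consequence is small.** There is no test, no threshold is stated for endoscopic remission, and event counts will be reported, so a reader could compute an exact interval. This stands, and it limits the weight of the point. It does not make the 95% label correct.
- **92.9% is one point on an oscillating curve.** True. The ranges around it average lower, at 92.1% and 91.6%.
- **Wilson has a drawback.** Its interval lies wholly above the truth 3.1% of the time at 5.8% and n=100. That rises to 4.6% over n=100 to 130 and 5.3% over true rates of 4% to 8%. For an efficacy claim this is the side that matters. It is a sound reason to prefer Clopper-Pearson, which holds each side at or below 2.5%.

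**Conclusion.** The point holds and should be fixed. At the plan's own 5.8% and n=100, the prescribed interval covers 92.9% rather than 95%, and its misses run about 13 to 1 (6.6% to 0.5%) towards an upper limit that is too low. The footnote is right that the lower bound is conservative, but it omits the upper limit and ties the problem to sample size, when the cause is the small number of events.

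The effect is modest. It understates how high the remission rate might be and does not create a false efficacy claim. Clinical remission, and the 90% and 73% in Section 10.2, are not affected. The 92.9% uses document values only; the wider ranges rest on assumed sample sizes and rates, because the enrolled number is not public and the true rate is unknown.

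**What to change.** **Wording.** In the Protocol Summary and Sections 10.4.2 and 10.4.6.3, add: *For endoscopic remission, the two-sided 95% confidence interval will be a Clopper-Pearson (exact) interval for a single proportion.* Wilson is an acceptable alternative if its above-truth miss rate is accepted.

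**Scope.** Name the same method for the endoscopic subgroup and forest-plot intervals, whose type Section 10.4.2 does not state, and for Week 12 endoscopic remission, which Section 10.4.6.3 puts under the Wald rule. No Week 12 endoscopic rate is given, so no coverage figure is claimed for it.

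**Table 10.2-2 at n=100.** Restate the row and say which kind of limit is shown:

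| Basis | Wald | Clopper-Pearson | Wilson |
|---|---|---|---|
| Plug-in at 5.8% | 1.22–10.4%, half-width 4.6% | 2.1–12.3%, half-width 5.1% | 2.7–12.2%, half-width 4.8% |
| Binomial average | 1.3–10.3%, half-width 4.5% | 2.2–12.3%, half-width 5.0% | not needed |

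The plug-in Clopper-Pearson limits are the beta quantiles evaluated at x=5.8.

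**Footnote.** Keep the statement on the lower bound. Add that with few events the normal approximation also gives an upper limit that is too low, and that this is not confined to samples under 100.

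**Clinical remission.** Wald can stay. Using the exact interval there is optional, for consistency only; the Section 10.2 probabilities of 90% and 73% would then become 93.8% and 81.6%.

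**Cost.** Wording, one table row and one footnote, settled before the data are analysed so that the choice cannot look driven by a low event count. Clopper-Pearson is mildly conservative (96.9%), and the half-width grows by about 0.5 percentage points on either basis (4.6% to 5.1%, or 4.5% to 5.0%). Sample size and data collection do not change.

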10.4.3 Secondary Endpoint(s)

The analyses of the key secondary endpoint (eg, pediatric clinical remission at Week 12) will be conducted in a similar manner as the co-primary endpoint.

10.4.5 Other Safety Analyses

All participants who take at least 1 dose of IP will be included in the safety analyses. AEs will be summarized by worst severity grade. AEs, with particular focus on TEAEs, will be summarized using the Medical Dictionary for Regulatory Activities system organ class and preferred term.

The incidence of TEAEs, IP-related TEAEs, TEAEs leading to discontinuation from treatment, events assessed as Common Terminology Criteria for Adverse Events (CTCAE) Grade 3 or Grade 4 (or moderate/severe if other rating scale is used), SAE, and AESIs (see Section 9.2.9) will be summarized for The incidence of TEAEs by severity and by relationship to study drug will also be summarized. SAEs will be presented by and by relationship to study drug. Summary tables will present incidence estimates and

Protocol Amendment No.: 02

[figure not shown]
individual event rates by system organ class as well as within each system organ class. Participants experiencing an event more than once with varying severity will be counted only once with the maximum severity within each system organ class/preferred term. For incidence of relationship to study drug, participants will be counted only once, in the category of the strongest relationship to study drug within each system organ class/preferred term. By-participant listings of death and AEs leading to death will be provided.

Laboratory values, vital signs, and ECG data will be presented in appropriate summary tables.

Cross tabulations will be provided to summarize frequencies of abnormalities.

Descriptive statistics will be provided for vital sign and body weight data.

By-participant listings will be provided for all relevant safety data. Graphical displays and figures will be provided where useful to assist in the interpretation of results.

10.4.6.2 Scoring Algorithms

Detailed algorithms on how to compute the CDAI scores and subscores are provided in the SAP.

10.4.6.3 Estimand Framework

For each key efficacy endpoint (ie, primary efficacy endpoint and secondary efficacy endpoints), the following primary estimand is specified following the final version of ICH E9 (R1) guidance (Adopted in May 2021). Other details on estimand will be provided in the SAP.

Treatment Condition of Interest

Adult equivalent doses of 0.46 mg and 0.92 mg of ozanimod will be evaluated

0.46 mg and 0.92 mg adult

equivalent doses will be determined

The participants are allowed to take concomitant medications (see Section 7.7) but are prohibited from taking some medications (see Section 7.7.2).

Population of Participants

Pediatric participants aged 2 to 17 years, inclusive, with moderately to severely active CD with an inadequate response, loss of response, or intolerance to prior therapy for CD are enrolled in this study.

Table 10.4.6.3-1: Variables to be Obtained for Each Participant

Measure	Endpoint
Primary – Efficacy	
PCDAI remission	Proportion of participants who achieve PCDAI < 10 at Week 64
SES-CD endoscopic remission	Proportion of participants achieving SES-CD \leq 2 or SES-CD \leq 4 points with no SES-CD subscore $>$ 1 point at Week 64
Secondary – Efficacy (Key)	
PCDAI remission	Proportion of participants who achieve PCDAI < 10 at Week 12
Secondary – Efficacy (Othe	er)
SES-CD endoscopic response	Proportion of participants who achieve a SES-CD decrease from Baseline of \geq 50% (ER-50) at Week 64
	Proportion of participants who achieve a SES-CD decrease from Baseline of \geq 50% (ER-50) at Week 12
PCDAI clinical response	Proportion of participants who achieve a decrease from Baseline in PCDAI score ≥ 12.5 and a total PCDAI score of < 30 points at Week 64
	Proportion of participants who achieve a decrease from Baseline in PCDAI score ≥ 12.5 and a total PCDAI score of < 30 points at Week 12
Symptomatic remission (adolescents only)	Proportion of participants who achieve an average daily abdominal pain score ≤ 1 point and average daily stool frequency ≤ 3 points with abdominal pain and stool frequency no worse than Baseline at Week 64
	Proportion of participants who achieve an average daily abdominal pain score ≤ 1 point and average daily stool frequency ≤ 3 points with abdominal pain and stool frequency no worse than Baseline at Week 12
Symptoms over time	Change from Baseline in stool frequency score over time
	Change from Baseline in abdominal pain over time

Protocol Amendment No.: 02

Table 10.4.6.3-1: Variables to be Obtained for Each Participant

Measure	Endpoint	
CDAI clinical remission	Proportion of participants who achieve CDAI score < 150 at Week 64	
(adolescents only)	Proportion of participants who achieve CDAI score < 150 at Week 12	
CDAI clinical response	Proportion of participants who achieve CDAI reduction from Baseline of ≥ 100 points or CDAI score < 150 at Week 64	
(adolescents only)	Proportion of participants who achieve CDAI reduction from Baseline of ≥ 100 points or CDAI score < 150 at Week 12	
Corticosteroid-free remission	Proportion of participants who achieve a PCDAI score < 10 at Week 64 while remaining corticosteroid free in the prior 12 weeks	
	Proportion of participants who achieve a CDAI score < 150 at Week 64 while remaining corticosteroid free in the prior 12 weeks (adolescents only)	
Endoscopic remission	Proportion of participants achieving SES-CD < 2 or SES-CD \leq 4 points with no SES-CD subscore > 1 point at Week 12	

Abbreviations: CDAI, Crohn's Disease Activity Index; ER-50, SES-CD decrease from Baseline of ≥ 50%; PCDAI, Pediatric Crohn's Disease Activity Index; SES-CD, Simple Endoscopic Score for Crohn's Disease.

Protocol Amendment No.: 02

Population-Level Summary

For each of the primary and secondary efficacy endpoints, the analysis will be based on the ITT population in which will be pooled. The estimated proportion along with its associated 2-sided 95% Wald CI using a normal approximation for a single sample proportion will be constructed.

